### 9.3 Study Design

This trial is a multi-strata Phase 2 study of IMG901. The primary endpoint will be objective response by RECIST criteria. As of Amendment #1, each stratum will accrue a maximum of 16 evaluable patients. IMG901 will be identified as having sufficient activity for further study in a particular stratum if there are at least 4 responses (PR or CR) confirmed by central review. This design will be used for all strata which have not been closed prior to the activation of Amendment #1.

We will consider the agent not of sufficient interest for further evaluation in a disease category if the true response rate is 15%. ( $H_0$  is a true response rate of 15%.)  $H_a$  is a true response rate of 40%. Each stratum will accrue 16 evaluable patients. Thus, there will be a maximum of 96 evaluable patients. If the agent has a true response rate of 15%, the rule described herein will identify the agent of sufficient activity for further study with probability 0.079 (Type I error). If the agent has a true response rate of 40%, the rule described herein will identify the agent of sufficient activity for further study with probability 0.833 (power against the alternative hypothesis  $p = 0.40$ ). In addition to making the decision to accept or reject the drug, the final results will be reported after all patients have been identified as having a CR, PR, or PD as their response according to protocol-specified criteria.

Prior to Amendment #1, the trial used a Simon two-stage optimal design in each stratum. The best response of disease was examined separately in each stratum. Within each stratum, the following two-stage design for 15% response rate vs. 40% response rate with  $\alpha = \beta = 0.10$  was employed:

	Cumulative Number of Responses at the End of the Stage	Decision
Stage 1: Enter 10 evaluable patients	0 or 1 2 or more	Terminate the trial for this stratum because the agent is ineffective. Proceed to Stage 2.
Stage 2: Enter 12 additional evaluable patients	5 or fewer 6 or more	Terminate the trial for this stratum because the agent is ineffective. Terminate the trial for this stratum because the agent is effective.

A comparison of the operating characteristics of the single stage and two-stage designs

appears below.

True response rate	Simon's optimal design (10 + 12 [2,6])			Single- stage design (16[4])

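### The success rule is written as 4 or more responses in 16, but the stated type I error, power and whole single-stage column belong to 5 or more; as written the type I error is 0.210 per stratum, not 0.079

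*Combined protocol and SAP*

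**What the plan says.** Section 9.3 sets out the single-stage design that applies, from Amendment #1, to every stratum not already closed: "each stratum will accrue a maximum of 16 evaluable patients". The drug is taken forward in a stratum "if there are at least 4 responses (PR or CR) confirmed by central review". The null hypothesis is a true response rate of 15% and the alternative is 40%.

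The same section then attaches operating characteristics to this rule. At 15%, "the rule described herein will identify the agent of sufficient activity for further study with probability 0.079 (Type I error"). At 40%, it will "identify the agent of sufficient activity for further study with probability 0.833".

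The comparison table heads its last column "Single- stage design (16[4"]) and lists probabilities of success for true rates from 5% to 50% in steps of 5 points. Beside it stands the earlier Simon two-stage design, labelled with the bracket [2,6]. The decision table for that design shows that 2 and 6 are the smallest counts that pass each stage.

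No other section gives a different threshold. Sections 9.1.1 and 9.5 refer the reader to Section 9.2 for the rule, but Section 9.2 covers only the tolerable dose and toxicity monitoring.

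**The concern.** A fixed sample size and a fixed threshold determine the type I error and power exactly, so the three parts of Section 9.3 (rule, prose figures, table column) can be checked against one another. A threshold of 4 in 16 is an observed rate of 25%, only 10 points above the null rate. With so few patients, a type I error as low as 0.079 looks implausible for that threshold.

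This is the rule applied to the primary endpoint. If the threshold and the figures describe different designs, the trial has two conflicting answers for a stratum with exactly 4 confirmed responses, and anyone relying on the stated 7.9% error is misled about how readily an inactive drug would pass. Section 9.1.1 allows detected activity to lead to further trials, and Section 2.6 foresees adding the drug to chemotherapy backbones if the efficacy targets are met.

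**Working it through.** **Inputs, all from Section 9.3.** n = 16 evaluable patients per stratum; written threshold r = 4; null rate 0.15; alternative rate 0.40; stated type I error 0.079; stated power 0.833.

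**Formula.** With X ~ Binomial(16, p), the probability of success is P(X ≥ r) = 1 − Σ C(16, k) p^k (1 − p)^(16−k), summed over k = 0 to r − 1.

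**Step 1: the written rule, r = 4.**

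- p = 0.15: the terms for k = 0 to 3 are 0.07425, 0.20965, 0.27748 and 0.22851, which sum to 0.78989. P(X ≥ 4) = 0.2101.
- p = 0.40: the terms are 0.00028, 0.00301, 0.01505 and 0.04681, which sum to 0.06515. P(X ≥ 4) = 0.9349.

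Neither matches the plan.

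**Step 2: reproduce the plan's figures with r = 5.** Subtract the term for k = 4.

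- p = 0.15: 0.21011 − 0.13106 = 0.0791, printed as 0.079.
- p = 0.40: 0.93485 − 0.10142 = 0.8334, printed as 0.833.

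**Step 3: the whole single-stage column.**

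| True rate | Printed | P(X ≥ 4) | P(X ≥ 5) |
|---|---|---|---|
| 5% | 0.001 | 0.007 | 0.0009 |
| 10% | 0.017 | 0.068 | 0.0170 |
| 15% | 0.079 | 0.210 | 0.0791 |
| 20% | 0.202 | 0.402 | 0.2018 |
| 25% | 0.370 | 0.595 | 0.3698 |
| 30% | 0.550 | 0.754 | 0.5501 |
| 35% | 0.711 | 0.866 | 0.7108 |
| 40% | 0.833 | 0.935 | 0.8334 |
| 45% | 0.915 | 0.972 | 0.9147 |
| 50% | 0.962 | 0.989 | 0.9616 |

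All ten printed values equal P(X ≥ 5) to three decimals; none equals P(X ≥ 4).

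**Step 4: could another design explain the figures?**

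- Searching all n from 5 to 40 and every threshold, only n = 16 with r = 5 gives both 0.079 and 0.833.
- Carrying over the old first-stage gate (at least 2 responses in the first 10, then at least 4 in 16) gives 0.193 at 15% and 0.915 at 40%, so it does not explain them either.
- The Simon columns reproduce with 2 and 6 as minimum passing counts (0.0907 at 15% and 0.9031 at 40%, printed as 0.091 and 0.903). The fault is therefore confined to the single-stage design. It also fixes the meaning of the brackets: read the same way, [4] is 4 or more, in agreement with the prose.

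**Step 5: size.**

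- Type I error: 0.2101 / 0.0791 = 2.7 times the stated value.
- Chance of exactly 4 in 16, the only count where the two versions disagree: 0.131 at 15%; 0.5950 − 0.3698 = 0.225 at 25%; 0.101 at 40%.
- If all three primary strata truly respond at 15% and are independent, the chance that at least one passes is 1 − (1 − 0.2101)³ = 0.51 under r = 4, against 1 − (1 − 0.0791)³ = 0.22 under r = 5.

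**The case against.** The arithmetic is not in dispute, and damaged text cannot account for it: the threshold appears twice (prose and column label), and both headline probabilities appear in prose and table. The reasonable objections concern what follows.

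- **Intent is not shown.** The prose and the label point to 4; the two probabilities and the column point to 5. A plausible cause is that 4 was entered in the calculation as the largest failing count and then written up as the smallest passing count, but the documents do not say so. This stands, and it is why both repairs are set out below.
- **Raising the threshold during the trial is more than a typing correction.** Section 9.1.1 records 10 Wilms, 8 rhabdomyosarcoma and 5 neuroblastoma patients enrolled before Amendment #1, and Section 12.2 requires the DSMC to approve major modifications. This also stands and affects how the change should be made.
- **The consequence is bounded.** The rule only marks a stratum for further study, follow-on trials are discretionary, Clopper-Pearson intervals will be reported regardless (Section 9.4), and only a count of exactly 4 changes the decision. True, but that count has a 10% to 23% chance at the three rates shown above, and the stated error rate is wrong whatever is observed.
- **Strata are judged separately and no family-wise control is claimed.** Correct. The three-stratum figures illustrate a scenario; the finding rests on the per-stratum error.

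**Conclusion.** The concern holds. As written, the rule has a type I error of 0.210 and a power of 0.935 per stratum, not 0.079 and 0.833. The stated figures and the whole single-stage column describe a threshold of 5. The written rule also has about twice the error rate of 0.10 that the two-stage design used before Amendment #1, and nothing in the plan suggests that such a loosening was intended or accepted.

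The result assumes only 16 evaluable patients with independent responses and a common response rate within a stratum, which is the model that reproduces the plan's own column. It applies to the strata not closed before Amendment #1. Since it concerns the decision rule for the primary endpoint, it must be corrected.

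**What to change.** Choose one of two repairs and state which was intended.

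1. **Threshold of 5.** Change the minimum number of centrally confirmed responses in Section 9.3 from 4 to 5 and relabel the column 16[5]. Every printed operating characteristic is then correct as it stands.
2. **Threshold of 4.** Keep the text and label, restate type I error as 0.210 and power as 0.935, replace the single-stage column with the P(X ≥ 4) values tabulated above, and justify a 21% false-positive rate per stratum.

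The first repair keeps the error and power that the plan reports. Whichever is chosen, the decision should be made without reference to response counts, before any stratum with exactly 4 responses is judged. It should be documented by amendment, with DSMC review under Section 12.2. The references in Sections 9.1.1 and 9.5 should point to Section 9.3 at the same time.

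The cost is a short text correction and its approval; no patients, visits or data are added.

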#### 4.1.1 Treatment Overview:

**NOTE:** Accrual of the first 6 patients is limited to Phase 1 Consortium institutions. Subsequent enrollments are open to COG institutions within the United States.

This will be a single-arm open label trial with three primary disease strata as outlined in the statistical section ([Section 9.0](#)) and three additional secondary strata for rarer cancers known to frequently express CD56.

All patients will receive IMG901 intravenously on Days 1 and 8 every 21 days. See [Section 4.1.4](#) for dose information. A cycle of therapy is 21 days. Treatment may consist of up to 17 cycles, for an approximate total therapy duration of 12 months, absent disease progression or unacceptable toxicity.

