## 9.0 STATISTICAL CONSIDERATIONS

### 9.1 Sample Size and Study Duration

#### 9.1.1 Patient Accrual and Expected Duration of the Study:

Three disease strata have been identified for reporting upon completion of evaluation of the particular disease stratum ('primary disease groups'). These disease strata are: (1) Wilms; (2) rhabdomyosarcoma; and (3) neuroblastoma. The evaluation rule is described in [Section 9.2](#) below.

In addition to the three main strata, enrollment into each of the following tumor groups ('secondary strata'): (4) pleuropulmonary blastoma, (5) malignant peripheral nerve sheath tumor, and (6) synovial sarcoma; will be open to accrual.

When the evaluation of the three primary disease groups is complete, enrollment to the study will be terminated unless the DVL committee leadership indicates further enrollment on the secondary strata is warranted.

If two of the three primary disease strata (Wilms, rhabdomyosarcoma, and neuroblastoma) have met their accrual and one remains open, the Cancer Therapy Evaluation Program (CTEP) and the ADVL1522 Investigators will discuss the study timeline.

Based on the enrollment rates prior to activation of Amendment #1, the following entry rates for the various tumors under study can be expected:

Disease Group/Strata	Patients/Year
1) Wilms tumor	18
2) Rhabdomyosarcoma	14
3) Neuroblastoma	9

For Wilms: 10 patients enrolled prior to activation of Amendment #1. Accrual of an additional 6 patients is expected to take approximately 4 months.

For rhabdomyosarcoma: 8 patients enrolled prior to activation of Amendment #1. Accrual of an additional 8 patients is expected to take approximately 7 months.

For neuroblastoma: 5 patients enrolled prior to activation of Amendment #1. Accrual of an additional 11 patients is expected to take approximately 14.5 months.

Allowing for roughly a 15% rate of ineligible/inevaluable patients, each stratum could need to enroll up to 19 patients to allow for 16 evaluable patients.

The study will likely require 2 to 3 years for sufficient patient enrollments to evaluate IMG901 in the three primary disease groups. If activity is detected in any category, further trials in subcategories of that category may be conducted at the discretion of the Developmental Therapeutics Steering and study committees. A maximum of 114 patients is anticipated.

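### Section 9.3 gives all six strata 16 evaluable patients and one power figure, but section 9.1.1 does not assure that number, or that power, for the three secondary strata

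*Combined protocol and SAP*

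**What the plan says.** Section 9.3 sets one single-stage design. It gives the stratum size first as a cap, "As of Amendment #1, each stratum will accrue a maximum of 16 evaluable patients", and then flatly: "Each stratum will accrue 16 evaluable patients. Thus, there will be a maximum of 96 evaluable patients". A stratum counts as showing sufficient activity "if there are at least 4 responses (PR or CR) confirmed by central review". The scope is general: "This design will be used for all strata which have not been closed prior to the activation of Amendment #1". The null rate is 15% and the alternative 40%, with a stated type I error of 0.079 and power of 0.833 and no distinction between strata.

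Section 9.1.1 treats the strata differently. Only Wilms tumor, rhabdomyosarcoma and neuroblastoma are named for reporting, and only these have expected entry rates (18, 14 and 9 patients a year) and completion times. Pleuropulmonary blastoma, MPNST and synovial sarcoma are simply open. Once the primary groups have been evaluated, "enrollment to the study will be terminated unless the DVL committee leadership indicates further enrollment on the secondary strata is warranted". Section 4.1.1 describes strata 4–6 as "three additional secondary strata for rarer cancers known to frequently express CD56".

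No section says how to read a secondary stratum that stops below 16 evaluable patients.

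**The concern.** The success bar is a fixed count of responses, not a proportion, so its power depends directly on how many evaluable patients a stratum has. Section 9.3 computes that power at 16 and attaches it to all six strata. For strata 4–6, section 9.1.1 makes closure the default and continuation the exception, and nothing in the documents shows that 16 patients each can be expected.

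If a secondary stratum closes short and is still judged against the 16-patient bar, missing the bar says little about the drug. A reader who relies on the printed power could take it as evidence of inactivity. These are rarer cancers, where such a false negative might not be retested.

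**Working it through.** **Inputs.** From 9.3: n = 16, success at 4 or more responses, null rate 0.15, alternative 0.40, printed type I error 0.079 and power 0.833. From 9.1.1: entry rates for strata 1–3 only, up to 19 enrolled per stratum to give 16 evaluable, and a study duration of 2 to 3 years. The number of evaluable patients at which a secondary stratum might close is not in the documents. It is an assumption, so a range is shown.

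**Formula.** Probability of meeting a bar of r responses among n patients at true rate p: P(X ≥ r) = Σ C(n,k) p^k (1−p)^(n−k), summed over k = r to n.

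**Step 1: the plan's own figures at n = 16.**

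| Bar | Type I error (p = 0.15) | Power (p = 0.40) |
|---|---|---|
| at least 4 (as written) | 0.210 | 0.935 |
| at least 5 | 0.079 | 0.833 |
| printed in 9.3 | 0.079 | 0.833 |

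The printed pair belongs to a bar of 5, not the written bar of 4. The whole single-stage column of the comparison table follows the bar of 5. At a 20% true rate, for example, 0.202 is printed; a bar of 5 gives 0.2018 and a bar of 4 gives 0.4019. The two-stage columns do reproduce (0.0907 and 0.9031 against the printed 0.091 and 0.903). In that design's [2,6] label the numbers mean 2 or more and 6 or more, so the [4] in the single-stage label reads as 4 or more. Because the cutoff is unresolved, both bars are carried forward.

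**Step 2: a secondary stratum closed at n patients.** Worked case, n = 8, p = 0.40:
- P(X ≤ 3) = 0.0168 + 0.0896 + 0.2090 + 0.2787 = 0.5941, so P(X ≥ 4) = 0.406.
- P(X = 4) = 70 × 0.4^4 × 0.6^4 = 0.2322, so P(X ≥ 5) = 0.174.

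| Evaluable n | Bar 4: type I error | Bar 4: power | Bar 5: type I error | Bar 5: power |
|---|---|---|---|---|
| 6 | 0.006 | 0.18 | 0.0004 | 0.04 |
| 8 | 0.021 | 0.41 | 0.003 | 0.17 |
| 10 | 0.050 | 0.62 | 0.010 | 0.37 |
| 12 | 0.092 | 0.77 | 0.024 | 0.56 |
| 16 | 0.210 | 0.935 | 0.079 | 0.833 |

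Within each bar, both quantities fall as n falls. At 8 patients and a 40% true rate, a bar of 4 misses the activity with probability 1 − 0.406 = 0.594, against 1 − 0.935 = 0.065 at 16.

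**Step 3: the accrual needed to fill a secondary stratum.** Taking the protocol's 2 to 3 years as the whole enrollment window, the need runs from 16/3 = 5.3 a year (16 enrolled, 3 years) to 19/2 = 9.5 a year (19 enrolled, 2 years). Neuroblastoma, the slowest primary stratum, is expected at 9 a year. The documents give no rate for strata 4–6 to set against this range.

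**The case against.** A reader might infer that the 9.3 figures cannot hold for strata 4–6. The documents do not support that. Committee leadership may extend secondary accrual, a stratum may fill before the primary groups are evaluated, and 9.3 also calls 16 a maximum. A small shortfall also costs little under the written bar of 4: power is 0.831, 0.876 and 0.910 at 13, 14 and 15 patients. What can be said is that the power is not assured.

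A reader might also infer that a short stratum will be declared inactive. No section says so. The current rule is worded as a condition for success, the lack-of-interest statement refers to a true rate rather than an observed count, and the explicit language of ineffectiveness sits in the superseded two-stage table. Against this, 9.3 does refer to a decision for or against the drug and exempts no stratum, so the ambiguity is real.

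Nor does early closure raise the false-positive risk. At a given bar, type I error falls.

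Some protection already exists. The totals of 96 evaluable and 114 enrolled are stated as maxima, and 9.4 already plans Clopper-Pearson intervals. The flat accrual sentence and the single power figure remain, as does the missing rule for a short stratum.

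**Conclusion.** The point stands in limited form. For strata 4–6, half of the strata, the stated power rests on an enrollment that 9.1.1 does not provide for. If such a stratum closed at 6 to 12 evaluable patients, power at a 40% true rate would be 0.18 to 0.77 with a bar of 4, or 0.04 to 0.56 with a bar of 5. Those closing sizes are assumptions. The harm is confined to false negatives, and arises only if a short stratum is read against the 16-patient bar.

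It would be wrong to conclude that 0.079 and 0.833 are correct for strata 1–3 and fail only for the secondary strata. With the written bar of 4 they are wrong for any stratum of 16: the type I error is 0.210, about 2.7 times the printed value (0.210/0.079). That mismatch is the more serious defect and must be settled first. The point about short strata holds whichever cutoff is chosen.

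**What to change.** 1. Reconcile the cutoff with its operating characteristics. If the rule is at least 4 of 16, replace the text figures with 0.210 and 0.935 and recompute the single-stage column. If it is at least 5 of 16, keep the figures and change the rule and the column label.
2. Then add to 9.3, in words such as:

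> The type I error and power given here apply to a stratum only if it reaches 16 evaluable patients. If a secondary stratum closes with fewer, its response rate will be reported with the Clopper-Pearson interval described in section 9.4, and no decision against the drug or finding of insufficient activity will be made. A finding of sufficient activity stands if the required number of centrally confirmed responses has already been reached.

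3. Reword the flat accrual sentence so that it agrees with the cap stated just before it.

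For the secondary strata this is a change of wording only, with no effect on enrollment or data collection. The cost is that a stratum closing early yields no formal negative conclusion.

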#### 9.4 Methods of Analysis

Response criteria are described in [Section 10.0](#). A responder is defined as a patient who achieves a best response (as defined in [Section 10.6](#)) of PR or CR on the study. Response rates will be calculated as the percent of evaluable patients who are responders, and Clopper-Pearson confidence intervals will be constructed.

Toxicity tables will be constructed to summarize the observed incidence by type of toxicity and grade. A patient will be counted only once per cycle for a given toxicity for the worst grade of that toxicity reported for that patient. Toxicity information recorded will include the type, severity, time of onset, time of resolution, and the probable association with the study regimen.

#### 9.5 Evaluability for Response

Any eligible patient who receives at least one dose of IMG901 will be considered evaluable for response with the following exception: if a patient receives non-protocol anti-cancer therapy (including surgery) during the response evaluation period after the patient is considered as having a partial or complete response but prior to confirmation of this status by tumor imaging and before progressive disease is noted, the individual will be considered inevaluable for the response endpoint. Further, patients who stop IMG901 after the first evaluation because of toxicities or death will be considered evaluable for the response evaluation and will be counted as non-responders for the response endpoint. Patients who demonstrate a complete or partial response confirmed by central review will be considered to have experienced a response for the application of the rule given in [Section 9.2](#). The evaluation period for determination of the best response will be 6 treatment cycles. All other patients will be considered non-responders. All patients considered to have a response (CR or PR) must have imaging studies reviewed centrally at the COG. Centers will be notified by the COG about requests for scans of patients with stable disease. See [Section 7.3](#) regarding shipping instructions. Preliminary assessment of activity using institutionally provided tumor measurements will be entered into CDUS quarterly. The central review by COG will be provided as the final reviewed assessment of response when such becomes available.

### 9.6 Evaluability for Toxicity

All patients who receive at least one dose of IMG901 according to protocol guidelines and either 1) experience a toxicity, or 2) complete the first cycle with no toxicity, will be considered in the evaluation of toxicity.

